**8. Study Design:**

a. Recruitment Methods

Potential subjects will be recruited at their preoperative office visit with their surgeon or, if applicable, during their inpatient stay prior to surgery. Informed consent will be obtained by the Spectrum Health Oncology Research staff. The potential subjects include all patients scheduled to undergo major oncologic surgery that meet all of the

inclusion criteria, and none of the exclusion criteria. There will be no payment to study subjects. We plan to enroll a total of 200 subjects, unless planned interim analyses determine otherwise.

b. Inclusion Criteria

- Subjects undergoing major oncologic surgery for standard of care purposes (to include, but not limited to: liver resections, radical cholecystectomy, pancreaticoduodenectomy (Whipple procedure), esophagectomy, gastrectomy, colectomy, and debulking with hyperthermic intraperitoneal chemotherapy, prostatectomies, nephrectomies, and partial nephrectomies)
- Male or female  $\geq$  18 years of age
- Subject agrees to participate in this study and provides informed consent

Exclusion Criteria

- Subjects with a history of hypercoagulopathy, deep vein thrombosis or pulmonary embolism
- Subjects that are on anticoagulation or antiplatelet medications at the time of surgery other than Aspirin
- Subjects with a history of TIA or Stroke
- Subjects with a history of atrial fibrillation
- Subjects with a known thrombus
- Baseline creatinine level greater than 2.83 mg/dL
- Subjects with known hypersensitivity to tranexamic acid
- Adults unable to provide informed consent
- Children
- Pregnant women
- Prisoners
- Non-English speaking subjects
- Any other medical condition including mental illness or substance abuse deemed by the investigator to be likely to interfere with a subject's ability to provide informed consent, cooperate and take part in this research study

c. Study Endpoints

The primary outcome measures will be operative blood loss and transfusion rates in subjects undergoing the eligible procedures. Secondary outcome measures will include cost of hospitalization, intensive care unit length of stay, and total hospital length of stay.

d. Procedures Involved in the Research

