The study design will be a randomized, double-blind, placebo-controlled trial. Following satisfaction of inclusion/exclusion criteria and enrollment into the study, designated pharmacy staff will be notified of the patient's enrollment and scheduled timing of surgery. Designated pharmacy staff will randomize the patient and assign the patient a unique study number. The subject will be randomized based on a predetermined algorithm by the pharmacy staff to receive preoperative intravenous tranexamic acid or preoperative intravenous isotonic electrolyte solution as placebo. The preparation will be indistinguishable by nursing, surgical, or anesthesia staff. The tranexamic acid group will receive a 1000 mg dose immediately preceding surgery, administered by the anesthesiologist. Both the tranexamic acid and placebo will be administered via intravenous piggyback over 15 minutes. Standard daily

laboratory measurements will continue unless clinical conditions necessitate more frequent monitoring. Transfusion will take place for hemoglobin levels < 7.0 g/dL or hemoglobin level < 10 g/dL with clinical symptoms indicating need for transfusion, per standard practice. Final decision on transfusion will be made according to the staff surgical oncologist's discretion.

Data to be recorded from operative records will include operative blood loss, operative time, amount of fluid received, and intraoperative transfusion requirements. Postoperative data including hemoglobin levels, transfusion requirements, surgical complications, thromboembolic events, length of ICU stay, length of hospital stay, and cost of inpatient stay. Subjects will be followed for 90 days postoperatively. Additionally, re-admission to the hospital during this time will also be recorded with associated complications.

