## **9. Statistical Plan**

### **a. Sample Size Determination**

We anticipate a 15-20% reduction in transfusion rates in the tranexamic arm when compared with placebo treatment. A sample size of 200 total subjects, 100 in each arm of the study, will be required to obtain a statistically significant result with  $p <0.05$ . Randomization will ensure an equal number of respective surgeries between the treatment and placebo arms of the study. All subjects who consent to the trial who meet the above inclusion criteria and complete the proposed dosing regimen will be included in the sample size.

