### **b. Statistical Methods**

Summary statistics will be calculated. Quantitative data will be expressed as the mean $\pm$ SEM and nominal data will be expressed as a percentage. Comparisons between groups for quantitative variables will be performed using the t-test. Nominal variables will be evaluated using the  $c^2$  test. Significance will be assessed at  $p<0.05$ .

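### Section 9.a guarantees equal numbers of each surgery per arm, but the documents describe no allocation method that would support the guarantee, and the tests in 9.b do not adjust for surgery type

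*Combined protocol and SAP*

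**What the plan says.** Section 9.a (Sample Size Determination) presents balance by operation as something the design secures: "Randomization will ensure an equal number of respective surgeries between the treatment and placebo arms of the study". The same section fixes the size: "A sample size of 200 total subjects, 100 in each arm of the study".

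The method of allocation appears only in section 8.d (Procedures Involved in the Research): "The subject will be randomized based on a predetermined algorithm by the pharmacy staff". Nothing there or elsewhere names strata, blocks, minimisation factors or surgery categories. Section 8.d says that pharmacy is told of the enrolment and of when surgery is scheduled. It does not mention the planned procedure.

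Section 8.b (Inclusion Criteria) names ten kinds of operation, from liver resection to partial nephrectomy, and leaves the list open: "to include, but not limited to: liver resections, radical cholecystectomy, pancreaticoduodenectomy (Whipple procedure" and so on. Section 8.c makes operative blood loss and transfusion rates the primary outcomes. Section 9.b plans t-tests for quantitative variables and chi-square tests for nominal ones, with no term for type of operation.

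**The concern.** Randomisation by itself does not make the number of each operation equal in the two arms. It makes the numbers equal in expectation, and any one trial departs from that by chance. Approaching equality within each type needs a device that uses the planned operation at the time of allocation, such as stratified blocks or minimisation. It also needs categories fixed beforehand, including a place for operations that the list does not name. The documents describe neither.

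Two things are at stake. First, readers of the protocol, and later of the results, are told of a balance that nothing written down secures. Second, blood loss and transfusion plausibly differ between operations as unlike as a partial nephrectomy and a debulking with hyperthermic chemotherapy. Chance differences in case mix then add noise to both primary comparisons, and the unadjusted tests in 9.b leave that noise in.

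**Working it through.** **Inputs from the documents.** 200 subjects, 100 per arm (9.a); ten named operation types, list open (8.b); significance at 0.05 (9.b); an anticipated reduction in transfusion of 15-20% (9.a), not said to be absolute or relative.

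**Inputs assumed, because the documents do not give them.** The case mix, transfusion rates by operation, the control rate, power and sidedness.

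**The plan's own figure.** The 200 cannot be reproduced from stated inputs, since control rate and power are missing. One assumed set does return it: 25% v 10%, two-sided 0.05, 80% power.

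n per arm = [1.96 × √(2 × 0.175 × 0.825) + 0.842 × √(0.25 × 0.75 + 0.10 × 0.90)]² / 0.15² = (1.053 + 0.443)² / 0.0225 ≈ 99.5, so 100.

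I use 25% v 10% below for that reason only. The point about balance does not depend on it.

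**Step 1: does unstratified allocation give equal numbers?** Assume ten types of 20 patients and arms fixed at 100.

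- One given type splits 10:10 with probability C(20,10) × C(180,90) / C(200,100) = 0.186.
- All ten do so with probability C(20,10)^10 / C(200,100) ≈ 5 × 10⁻⁷.
- At least one type splits 14:6 or worse with probability about 0.62.
- The median of the largest between-arm difference in any type is 8 patients. Unstratified blocks of 4 give the same median.
- With an assumed uneven mix (50, 40, 30, 20, 15, 15, 10, 10, 5, 5) the median is again 8, and types with an odd count cannot be equal at all.

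**Step 2: how far can this move the transfusion comparison?** Assume 60 of the 200 operations are high-bleeding, with a transfusion rate 30 points above the rest, and an overall control rate of 25%. The group rates are then 25 + 0.7 × 30 = 46% and 25 − 0.3 × 30 = 16%.

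- The number of high-bleeding operations in one arm is hypergeometric with SD 3.25. The between-arm difference is twice the deviation, so its SD is 6.5 patients.
- A shift of one SD is 6.5/100 × 30 ≈ 1.9 points.
- A 35:25 split or worse, in either direction, has probability about 0.16. A 35:25 split shifts the difference by 10/100 × 30 = 3 points.
- The standard error of the transfusion difference at 25% v 10% is √[(0.1875 + 0.0900)/100] = 5.3 points. Case mix therefore contributes about 1.9² / 5.3² = 3.6/28 ≈ 13% of the variance.

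**Step 3: what does that do to the test?** Simulation of the step 2 scenario with two procedure groups, arms of 100 and 40,000 trials per run:

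| Allocation | Test | Type I error | Power, 15-point reduction |
|---|---|---|---|
| Unstratified | Unadjusted chi-square | 4.7-5.0% across runs | 82% |
| Stratified | Unadjusted chi-square | about 3.7% | 83% |
| Either | Mantel-Haenszel by group | about 5% | 87% |

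The simulated 82% differs slightly from the formula's 80% because the formula is approximate and ignores the two-group mix. The comparison between rows is what matters.

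**The case against.** The strongest reply is that the algorithm in 8.d is simply not described. Read together with 9.a, it could well be stratified by operation, in which case the gap is one of reporting. That stands. A reader might infer that the trial was allocated without regard to operation, but the documents do not show this. The short list of what pharmacy is told does not settle it, because 8.d does not say that the list is complete.

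A reader might also infer that the open list makes balance unattainable. It does not: minimisation, or a stratum for other operations, copes with it. There is no need to narrow eligibility, and doing so could slow accrual when section 7 counts about 15 such operations a month.

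The third tempting inference is that imbalance would invalidate the unadjusted tests. It would not. Chance imbalance under randomisation is already part of their sampling error, and the simulated type I error is close to 5%. A 3-point shift is a tail event on assumed inputs.

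Finally, stratifying alone gains almost nothing (82% to 83%), and rewording 9.a alone would remove the misstatement. Both are true. They are reasons to pair stratified allocation with an adjusted analysis. What remains is that 9.a states a certainty for which the documents provide no means, and that 9.b gives up precision that is cheap to recover.

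**Conclusion.** The concern holds in a limited form. The documented design does not support the guarantee in 9.a. Unless the undescribed algorithm uses the planned operation, balance by surgery type holds only on average. Even stratified blocks would give approximate balance, and sections 8.g and 9.a then leave out some randomised subjects who do not complete dosing, which can disturb it again.

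The cost is precision. In the assumed scenario it is about 5 points of power (82% against 87%), nearly all of it recovered by the analysis. The size rests on the assumed share of high-bleeding operations, the 30-point gap in rates, the 25% control rate and a 15-point absolute reduction. A smaller gap between operations would shrink it. The 62% chance of a 14:6 split or worse rests on ten equally common types. That the guarantee is unsupported rests on none of these assumptions.

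**What to change.** - **8.d:** have pharmacy randomise in permuted blocks within a few broad groups of planned procedure. Assign every other eligible operation to one of the groups, or to an 'other' group, before randomisation. Leave 8.b unchanged. If the algorithm already works this way, name its strata and blocks.
- **9.a:** replace the sentence with: *Randomisation is stratified by planned procedure group, so that arms are approximately balanced within groups.*
- **9.b:** analyse by the same groups, for example Mantel-Haenszel for transfusion and a linear model with group terms for blood loss. This has to accompany the change in 8.d, because stratified allocation followed by unadjusted tests is conservative (about 3.7% against a nominal 5%).

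The cost is a short amendment. Enrolment staff must pass the planned procedure group to pharmacy, and pharmacy must keep a few separate lists. No additional patients are needed.

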### **b. Statistical Methods**

Summary statistics will be calculated. Quantitative data will be expressed as the mean $\pm$ SEM and nominal data will be expressed as a percentage. Comparisons between groups for quantitative variables will be performed using the t-test. Nominal variables will be evaluated using the  $c^2$  test. Significance will be assessed at  $p<0.05$ .

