**f. Provisions to Monitor the Data for the Safety of Subjects**

Adverse events including thromboembolic events and development of acute renal failure will be monitored and recorded on a weekly basis by study personnel. In the event an increased number of unanticipated events occur, the study will be temporarily stopped pending review. Review of unblinded data will be performed by an independent clinician, pharmacist, and statistician to determine the need to discontinue or resume the study. If a significant increase in adverse events is noted in the treatment arm, the trial will be terminated. Decisions resulting from the review will be discussed with the primary investigator.

Interim reviews of unblinded data for statistically significant findings will be performed by an independent clinician, pharmacist, and statistician after every 50 subjects complete the study. Findings will be reviewed with the investigators, and decisions will be made as to whether or not the research study continues. These interim reviews and outcomes will be reported to the IRB.

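### Surgery type is said to be balanced by randomisation but is left out of both primary analyses, which costs power if it predicts outcome; state the allocation restriction and adjust for procedure group

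*Combined protocol and SAP*

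**What the plan says.** Section 8.c names two primary outcomes, operative blood loss and transfusion rates.

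Three other places bear on surgery type:

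- **Section 8.b, inclusion criteria.** The eligible surgery is an open list, "to include, but not limited to: liver resections, radical cholecystectomy" and eight further named procedures, ten in all.
- **Section 8.d, procedures.** "The subject will be randomized based on a predetermined algorithm by the pharmacy staff". No stratification factor, block size or minimisation rule follows.
- **Section 9.a, sample size.** "Randomization will ensure an equal number of respective surgeries between the treatment and placebo arms of the study". No mechanism is given.

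Section 9.b sets the analysis: "Comparisons between groups for quantitative variables will be performed using the t-test". Nominal variables are compared by chi-square, and the threshold is p<0.05. No adjusted or stratified analysis appears anywhere in the document.

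**The concern.** Sections 8.d and 9.a do not fit together. Simple randomisation cannot guarantee equal numbers of each surgery per arm. So either allocation is restricted by surgery type in a way the plan does not describe, or section 9.a states an expectation as a guarantee.

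Under either reading, the analysis leaves out a factor that the sponsor thought worth balancing, in a population that runs from prostatectomy to liver resection and debulking surgery.

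- **Restricted allocation, prognostic procedure.** The arms are balanced on procedure, but the unadjusted standard error still contains the between-procedure variance. It is too large, the true type I error falls below 5%, and the reported p-values and SEMs do not reflect the design.
- **Simple allocation, prognostic procedure.** The t-test and chi-square hold their level but are less efficient than an adjusted analysis of the same data.

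What is at stake is power at a fixed 200 subjects, not false-positive control.

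**Working it through.** **Inputs from the plan.** 200 subjects, 100 per arm (9.a); significance at 0.05, sidedness not stated, taken here as two-sided (9.b); ten or more procedures (8.b). **Assumed, because the plan does not give them:** the share of outcome variance explained by procedure (R²), outcome distributions, rates by procedure, the effect on blood loss, and power. Transfusion rate is read as the proportion of subjects transfused.

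**The plan's own figure.** The 200 cannot be checked, since neither the placebo rate nor the power is stated. It matches some absolute reductions: 25% vs 10% at 80% power needs 100 per arm, and 60% vs 40% needs 97. It does not fit a relative reduction of 15–20%: for placebo rates of 20–80%, 80% power needs 123 to 2,629 per arm. That is a separate matter and does not affect this point.

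**Step 1: closed form for a quantitative outcome.** The unadjusted SE exceeds the adjusted SE by k = 1/√(1−R²). Set the adjusted analysis at 80% power, so its expected z is 1.96 + 0.8416 = 2.8016.

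- Restricted: alpha = 2(1−Φ(1.96k)); power = 1−Φ(1.96k−2.8016).
- Simple: alpha about 5%; power = 1−Φ(1.96−2.8016/k).

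| R² | k | alpha, restricted | power, restricted | power, simple |
|---|---|---|---|---|
| 0.05 | 1.026 | 4.4% | 78.5% | 78.0% |
| 0.1 | 1.054 | 3.9% | 76.9% | 75.7% |
| 0.2 | 1.118 | 2.8% | 72.9% | 70.7% |
| 0.4 | 1.291 | 1.1% | 60.7% | 58.3% |

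Example, R² = 0.2, restricted: 1.96 × 1.118 = 2.191; 2.8016 − 2.191 = 0.610; Φ(0.610) = 72.9%.

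**Step 2: the same comparison with a different anchor.** Fix the effect at 0.396 SD of the total spread, which gives the t-test 80% power when procedure is not prognostic. Under restricted allocation, t-test vs adjusted power is 81.3 vs 84.0% (R² 0.1), 82.7 vs 87.9% (0.2) and 86.1 vs 95.1% (0.4). The gap at R² = 0.4 is then 9 points rather than 19. Under simple allocation it is about 15 (80 vs 95%).

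**Step 3: blood loss by simulation on the raw scale.** Eight procedure groups, lognormal, within-group log-SD 0.7, between-group log-SD 0, 0.2, 0.35 or 0.5, a 25% reduction, 6,000 trials per cell. Restricted means permuted blocks of 4 within group; simple means 100:100 without strata. Power, t-test vs linear model with procedure group:

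| Raw-scale R² | restricted | simple | t-test type I error, restricted / simple |
|---|---|---|---|
| 0 | 72.0 vs 72.2 | 74.4 vs 72.5 | 5.4% / 5.0% |
| 0.06 | 68.8 vs 70.6 | 67.2 vs 69.4 | 4.0% / 5.0% |
| 0.15 | 61.2 vs 67.7 | 60.8 vs 66.1 | 3.4% / 5.4% |
| 0.24 | 51.7 vs 63.3 | 51.6 vs 63.0 | 2.2% / 4.6% |

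Simulation error is about √(0.7×0.3/6000) = 0.6 points per cell. A more extreme case (R² 0.38), outside the range relied on here, gave 56.9 vs 76.7% restricted and 55.1 vs 74.0% simple.

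**Step 4: transfusion by simulation.** Five groups, common odds ratio 0.4, 200 subjects. Power, chi-square vs Cochran-Mantel-Haenszel (CMH):

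| Placebo rates, lowest–highest group | restricted | simple | chi-square type I error, restricted |
|---|---|---|---|
| all 35% | 80.7 vs 80.5 | 80.9 vs 79.9 | 5.3% |
| 20–50% | 77.8 vs 78.7 | 76.3 vs 77.2 | 4.8% |
| 10–50% | 71.3 vs 73.7 | 69.7 vs 71.7 | 4.0% |
| 8–70% | 69.4 vs 75.9 | 68.3 vs 75.0 | 3.2% |
| 5–80% | 58.5 vs 72.0 | 57.6 vs 71.2 | 1.8% |

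Under simple allocation the chi-square type I error stayed at 4.5–5.5%. The widest row depends on how rates are spaced between the extremes: evenly spaced strata gave 66 vs 76%.

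**Step 5: transfusion with overall rates held at 35% vs 17.5%.** Four equal groups, 10,000 trials. Placebo rates of 15/25/40/60% gave 82.1 vs 85.2% restricted and 81.1 vs 85.4% simple. Rates of 5/15/45/75% gave 84.9 vs 91.6% and 80.2 vs 90.7%. With no prognostic effect both tests gave about 81%.

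**The case against.** The strongest reply is that this is a choice of efficiency, not validity. The planned tests are valid under simple allocation and conservative under restricted allocation, and nothing in the documents shows how strongly procedure predicts either outcome. In the mild scenarios the loss is 1.5 to 2 points (closed form, R² 0.05) or about 1 point (transfusion, strata 20–50%). This stands, and it is why the point is a recommendation and not a fault that invalidates the trial.

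Three further points have some force:

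- **Anchor.** Starting from 80% adjusted power makes the planned tests look as if they fall short of a target. The plan states no power and plans no adjusted test. Step 2 shows that balancing procedure does not push the t-test below its planned power; the loss is relative to a better analysis of the same data.
- **Moving scenarios.** In steps 3 and 4 the spread or overall rate changes from row to row, so only differences within a row are meaningful. Step 5 holds the overall rates fixed and still shows gains of 3.1 to 10.5 points.
- **Restricted branch.** Section 9.a may express only expected balance. The below-nominal alpha figures then do not apply, but the power loss under simple allocation remains.

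It is also fair that section 8.d does not list procedure type among the data to be recorded, so the remedy may need one data item as well as wording.

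**Conclusion.** The concern holds. The plan asserts balance by surgery type without a mechanism and omits surgery type from both primary analyses. False positives are not inflated; the cost is power, and under restricted allocation also p-values and SEMs that do not match the design.

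Comparing within rows of steps 3 and 4, adjustment changes power by about -2 to +12 points for blood loss and -1 to +14 points for transfusion. The losses occur only where procedure is not prognostic. The larger gains need marked differences between procedures, which are plausible for so mixed a list but are not documented. All sizes rest on assumed variances, rates and effects; the direction does not, given that procedure is prognostic. Confidence in the size is therefore moderate. The case for acting rests on the asymmetry: at most about 2 points lost against a possible double-figure gain at the same sample size.

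**What to change.** 1. In the randomisation text, state whether allocation is restricted by surgery type and, if so, by which groups and block sizes. Align section 9.a with it.
2. Before the first unblinded review, which is due "after every 50 subjects complete the study", prespecify a few procedure groups based on the procedure scheduled at randomisation. Use the randomisation strata if there are any, and pool rare procedures.
3. Analyse operative blood loss by a linear model with arm and procedure group; report the adjusted mean difference with 95% CI.
4. Analyse the proportion transfused by CMH over the same groups; report a stratified risk difference with 95% CI.
5. Keep the unadjusted t-test and chi-square as sensitivity analyses.

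Separate and optional: if blood loss proves right-skewed, prespecify a stratified rank test or an adjusted log-scale model as a secondary analysis. Include a rule for zero values, and note that the log model estimates a ratio of geometric means rather than the mean difference.

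**Cost.** Changes to the wording of the randomisation and analysis sections. The procedure is known for every subject, but the scheduled procedure should be added to the recorded data and, if allocation is stratified, passed to pharmacy at enrolment. Pooling is necessary: ten procedures would average 200/10 = 20 subjects each at the end and 50/10 = 5 at the first review. If procedure is not prognostic, adjustment cost 0 to 2 points of power in the simulations.

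### Operative blood loss, a primary outcome pooled over very unlike operations, is compared by an unadjusted t-test that ignores operation type and skew; this probably costs power, not validity

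*Combined protocol and SAP*

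**What the plan says.** Section 8.c: "The primary outcome measures will be operative blood loss and transfusion rates in subjects undergoing the eligible procedures". Section 8.b gives an open-ended list of eligible operations. It starts with liver resection and runs through pancreatic, oesophageal, gastric and colon surgery to "debulking with hyperthermic intraperitoneal chemotherapy, prostatectomies, nephrectomies, and partial nephrectomies".

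Section 9.b is the entire analysis. "Quantitative data will be expressed as the mean" with its SEM, and "Comparisons between groups for quantitative variables will be performed using the t-test". It names no transformation, rank test, covariate or sensitivity analysis. The recorded scale is implied by the mean and SEM; the text mentions neither millilitres nor untransformed data.

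Section 9.a sets the size: "A sample size of 200 total subjects, 100 in each arm of the study". The only effect offered in support is on the other primary outcome: "We anticipate a 15-20% reduction in transfusion rates in the tranexamic arm". The same section says randomization will give the arms equal numbers of each kind of operation. Section 9.b makes no use of that.

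**The concern.** Blood loss cannot fall below zero and usually has a long upper tail. Pooling small and large operations lengthens that tail. A difference in raw means then depends heavily on a few cases, and its size depends on which operations happened to enrol.

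Operation type adds a second problem. If the arms are balanced on type, the differences between types drop out of the treatment comparison but stay in the t-test's error term. The test then acts as if the estimate were noisier than it is. At stake is the chance of detecting a real effect on a primary outcome for which the plan shows no power calculation.

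**Working it through.** **The plan's own figure.** The 200 rests on transfusion rate, with no control rate or power stated, so it cannot be reproduced uniquely. One pair that fits is 25% v 10% (two-sided 5%, 80% power): [1.96√(2×0.175×0.825) + 0.842√(0.25×0.75 + 0.10×0.90)]² / 0.15² ≈ 100 per arm. None of this bears on blood loss.

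**Inputs.** From the documents: 100 per arm, significance level 0.05, t-test. Assumed: two-sided testing, lognormal loss, log SD 0.5-1.2, and a proportional reduction of 20-40%.

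**Step 1: scale alone, one lognormal population.** For a t-test on log loss, power ≈ Φ(−ln(1−r)/(s√(2/100)) − 1.96), where r is the reduction and s the log SD. With r = 0.30 and s = 1.0: 0.357/0.1414 = 2.52, so Φ(0.56) = 71%. Simulation at a 30% reduction:

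| log SD | raw t | log t |
|---|---|---|
| 0.8 | 77% | 89% |
| 1.0 | 51% | 71% |
| 1.2 | 34% | 55% |

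Over reductions of 20-35% the gap is mostly 10-20 points at log SD 0.8-1.0 (about 7 at log SD 0.8 with a 35% cut). It is 0-7 points at log SD 0.5-0.6. At log SD 1.2 it starts at 10 and peaks at 26 to 28, depending on the simulation run. Null rejection of the raw t-test is 4-5%.

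**Step 2: influence of large bleeds.** In a lognormal sample of 200, the five most extreme values carry a median 45% (log SD 0.8) to 55% (log SD 1.0) of the total sum of squares.

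**Step 3: operation type.** Assume four types with medians 100, 250, 500 and 900 mL, shares 30/30/25/15%, within-type log SD 0.7, and exact balance between arms. The between-type log variance is 0.61, so the total log SD is √(0.61 + 0.49) = 1.05.

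- Log scale: the true SE of the difference is 0.7 × 0.1414 = 0.099, but the unadjusted test uses 1.05 × 0.1414 = 0.148. Its effective critical value is 1.96 × 0.148/0.099 ≈ 2.94, so it rejects about 0.3% under the null.
- Recorded scale: type means are the medians × e^0.245, i.e. 128, 319, 639 and 1150 mL. The within-type SD is about 461 mL and the total SD about 575 mL. The effective critical value is 1.96 × 575/461 ≈ 2.45, or about 1.4% under the null. Simulation gives about 1%.
- Log scale adjusted for type, 30% cut: 0.357/0.099 = 3.60, so Φ(1.64) = 95%.

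Simulated power for a uniform 30% cut, balanced mix:

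| | unadjusted | adjusted for type |
|---|---|---|
| raw | 55% | 73% |
| log | 73% | 95% |

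If type varies freely instead, the unadjusted tests give 54% (raw) v 66% (log), with null rejection near 5%.

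**Step 4: non-uniform effects.**

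- A 40% cut only above the 75th percentile, log SD 0.8: raw 54%, log 23%.
- Cuts of 10/20/30/40% from smallest to largest operation, same mix: unadjusted raw 56-59%, unadjusted log 44-45%, log adjusted for type 75%.
- A steeper gradient of 0/10/30/40%, both analyses adjusted, by normal approximation. Log: mean effect 0.3×0 + 0.3×0.105 + 0.25×0.357 + 0.15×0.511 = 0.197; 0.197/0.099 = 1.99; power about 51%. Millilitres: mean effect 0.3×32 + 0.25×192 + 0.15×460 ≈ 127 mL; SE about 55 mL; 127/55 ≈ 2.3; power about 63%.

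**The case against.** The strongest reply is that all of this rests on assumptions the documents do not supply. That is correct. A reader might take a loss of 10-20 points as a property of this trial; no blood-loss variability or effect is given, and at log SD 0.5-0.6 the loss nearly vanishes.

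A second reply is that absolute volume is a legitimate target. The Background is about operations with substantial bleeding, and section 11 ties less blood loss to fewer transfusions. A ratio of geometric means answers a different question. This also stands, and it is why a millilitre analysis belongs in the plan.

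A third is that changing the scale alone is not reliably better. Step 4 confirms it: a moderate gradient across operations is enough for the unadjusted log test to lose to the raw one. A reader might infer that the remedy is simply to take logs. The figures do not support that. In step 3, adjusting for type on the recorded scale gains as much as taking logs does.

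Finally, section 9.a promises balance by operation. That limits chance imbalance in case mix, though not in large bleeds within a type. It does not rescue the planned analysis: balance that the analysis ignores makes the t-test conservative.

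**Conclusion.** The point holds as a loss of efficiency and as sensitivity to a few large bleeds. Under a uniform 20-35% reduction in lognormal loss, the raw t-test gives up roughly 10-20 points against a log t-test at log SD 0.8-1.0, with a tested range of 0-28 points over log SD 0.5-1.2. The ranking reverses if the benefit is concentrated in larger operations or bleeds. In the assumed balanced mix, the planned test has about 55% power for a 30% cut, against 95% for a log model adjusted for type. Under the 10/20/30/40% gradient the comparison is 59% v 75%. Those contrasts change both scale and adjustment.

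A reader might infer that the t-test is invalid or yields false positives. It does not: null rejection was 4-5% without balancing by type and about 1% with it. Exact balance is itself an assumption, because section 8.d mentions only a predetermined algorithm. That the analysis is in raw millilitres is a reasonable inference, not a stated fact.

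This is a worthwhile, low-cost improvement rather than a fatal flaw.

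**What to change.** Amend section 9.b before unblinding. Because section 8.f schedules unblinded reviews after every 50 subjects, that means before the first of them if possible. Suggested wording:

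> Operative blood loss is compared with a linear model on the log scale adjusted for operation type (zero or minimal entries set to a fixed floor chosen before unblinding) and reported as an adjusted ratio of geometric means with 95% CI. The difference in mean mL adjusted for operation type and a Wilcoxon test stratified by operation type are supportive.

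Since the list of operations is open-ended, the categories used for adjustment should be fixed at the same time.

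The cost is a few sentences and no new outcome data. The downside is that the main effect becomes a ratio rather than a volume, and the log scale is weaker than an adjusted millilitre analysis if the drug acts mainly in the largest operations or bleeds. The adjusted millilitre difference is kept for that reason.
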